5.5 General analysis principles

The analysis of primary, secondary, and, where possible, additional outcomes will be adjusted for the stratification factors which were used during randomisation, centre, and ability to speak English, only. All main analyses will be performed on a complete case basis (ignoring missing data) for the outcomes in question. A missing category will be created for the only covariate in the models "ability to speak English". The significance for statistical tests (alpha) will be 5%, all confidence intervals will be presented at the 95% level and all p-values will be two-sided. As the intervention arm includes group pregnancy circles, clustering will be accounted for in the intervention arm using pregnancy

circles as the units of clustering, while participants in the control arm will be modelled as a cluster size of one [1].

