5.8 Estimand Framework

Inference on the primary and secondary outcomes is complicated by the potential occurrence of intercurrent events. An intercurrent event is defined as an event that happens after randomisation which either affects the measurement, interpretation or existence of an outcome. The 2020 ICH E9 R1 addendum lays out a framework for providing a clear description of the treatment effect to be estimated from a trial (11). The table below describes the treatment effect to be estimated for REACH using the estimand framework.

Estimand framework summary for primary outcome

P	Population	Variable	Summary	Treatment	Detential
			Measure	rreatment	Potential Intercurrent Events*
objective is to demonstrate superiority of Pregnancy Circles over standard individual antenatal care on the health of babies. The primary comparison of having a healthy baby (yes/no) will be made regardless of whether women withdraw from the assigned antenatal care or	Pregnant women registering for antenatal care with NHS maternity services excluding women defined in the exclusion list of section 6 of the trial protocol. All women who during the pandemic were not able to receive the intervention or were only able to receive a low dose of intervention are excluded.	The "healthy baby" composite consists of the following 4 components: 1. Live baby (i.e. no pregnancy loss before or after 24 completed weeks and no neonatal death within 28 days of the birth) 2. Born at term (37 weeks and above) 3. Appropriate weight for gestational age (GROW centile >9.99 & <90.01) 4. Not admitted to a neonatal care unit (which includes Intensive Care Unit, SCBU and High Dependency Unit, but NOT transitional care) A baby is considered a "healthy baby" only if the answer to all above	Marginal Odds ratio and risk difference.	Pregnancy circles groups composed of 8 to 12 women during 8 sessions of 2 hours from week 16 of pregnancy (roughly 1 session every 17.5 days).	Intercurrent Events* Woman stops intervention at any point for any reason Develop complications and become higher risk — woman ask to have 1-2-1 Change of service because of pandemic or relocation Rates of induction going up Woman switches circle before attending first antenatal care session Woman switches circle after attending first antenatal care session

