5.14 Dose response analysis

We will explore the dose-response relationship between the number of sessions attended and the primary outcome in the intervention arm. The scale of this attendance variable is 0-8 where 0 = no antenatal circles attended and 8 = 8 antenatal circles attended. Dose will be used as a continuous variable assessed in a model fitted on intervention group participants only.

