5.16.4 The effect of COVID-19 pandemic

A further analysis will be conducted to estimate the intervention effect accounting for the different phases of the COVID-19 pandemic (14). Using the primary outcome analysis described in 5.10, the effect of the trial intervention on the 'Healthy baby' criteria will be compared to the control intervention in each phase. Five phases – pre-pandemic, no dose, low/very low dose, moderate/high dose, and post-pandemic – will be used to perform a fixed-effect meta-analysis with inverse-variance weighting. The phase participants are categorise in depends on the overlap of their intervention period with pandemic periods of varying restriction and has been pre-specified (see appendix 8.3). Participants concurrently randomised into the control are categorised in the same way. Further details on the impact of covid and the definition of the dose received can be found in the appendices.

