In line with government and NIHR guidance, we paused all recruitment for the Pregnancy Circles trial from the 18th March 2020. At this point we had recruited 1624 from our target of 1732. NHS Trusts suspended all in person group based activities and women in the Pregnancy Circles were offered one to one care. We encouraged sites to consider virtual options to continue the Circles and presented a number of other options to continue care that would be underpinned by the values of the Pregnancy Circles model (Box 1).

Options for continuing Pregnancy Circles during the pandemic

- Encourage women to continue peer support through their What's App group.
- Continuing to facilitate the groups virtually as per the schedule in the manual, using
 a separate clinical WhatsApp group or other technology (ask us if you would like
 some suggestions). Without the self-checks and palpations, session length would
 be reduced. The 'core values' of Pregnancy Circles (see below) can be extended to
 virtual meetings)
- Any virtual facilitation could be done by a single midwife, and this could be done by midwives who have to self-isolate but could still work from home.
- Pregnancy Circle women have learned how to self-monitor, and this may offer services an opportunity in providing more virtual group care and fewer 1-1:
 - Could you provide the women with a supply of urine sticks for use at home?
 - Could you support women who choose to buy home blood pressure machines to send you regular readings?
- If virtual group care is not a possibility, consider whether continuity from one of the facilitating midwives could be extended in 1-1 appointments.

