At the point of lockdown, 45 Pregnancy Circles had been run and completed, a further 58 circles were either already running or recruited to, and around six circles were waiting to be recruited to. Of the 58 already running or recruited to, 33 Circles have been assessed as providing a high or moderate dose of the COVID-19 adapted Pregnancy Circles during lockdown. From our target sample size of 1732 we had recruited 1624 women. We estimate that of the target sample size, 46% (n=795) received a 'full dose' of the intervention prior to the pandemic. A further 31% (n=531) had received a high or moderate 'dose' during the pandemic, 10% (n=176) had received a low or very low 'dose'; 7% (n=122) received no intervention; and 6% (n=108) were still to be recruited.

Pregnancy circle 'dose' offered

	Total groups	Details of dose offered	Total participants	Total intervention
	(Pregnancy Circles)		(int + control)	participants
Intervention as planned	45 (estimate)		795 (46% of sample size)	395
Partial intervention during lockdown	33	High 12 Circles (all had met face to face – 7 for 4 or more sessions; 5 who had met face to face fewer times but and then followed up with the provision of virtual groups/whatsapp/ continuity etc) Moderate 21 Circles (This category was either those that had met 3-4 times face to face and then had little in lockdown (8) OR Had met 1-2 times plus had other components (10). There were also 3 Circles that had not met face to face at all, but offered virtual circles)	531 (31%)	271 (117 high 154 moderate)
Low intervention during lockdown	13	Very low 6 Circles (Did not meet in person or virtually, but had 1 intervention component e.g. continuity of carer only) Low 7 Circles (2 Circles had met once, but nothing in place after; the remaining 5 did not meet face to	176 (10%)	92 (31 very low; 61 low)

		face nor offered any virtual groups, but had continuity and one other aspect eg Whatsapp group)		
Recruited but received no intervention	12	12 Circles; none of these circles had met face to face and no additional intervention components offered during lockdown. (most mid recruitment)	122 (7%)	63
Not yet recruited	-	-	108 (6%)	-

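### The exploratory dose-response model has no term for pandemic phase, so part of any pandemic-period difference in outcome could appear as an effect of sessions attended

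*SAP*

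**What the plan says.** Section 5.14 announces the analysis as exploratory: "We will explore the dose-response relationship between the number of sessions attended and the primary outcome in the intervention arm". The scale is 0 to 8 sessions. "Dose will be used as a continuous variable assessed in a model fitted on intervention group participants only". No covariate is named.

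The general rule in 5.5 is that analyses "will be adjusted for the stratification factors which were used during randomisation, centre, and ability to speak English, only".

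Appendix 8.3 describes what lockdown did: "NHS Trusts suspended all in person group based activities and women in the Pregnancy Circles were offered one to one care". It classes 33 affected circles, with 271 intervention women, as moderate or high dose. Sections 4.1.2 and 5.8 keep these women in the primary analysis and exclude the low-, very-low- and no-dose women. Section 5.14 does not say which set it uses.

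Pandemic phase is used elsewhere, but only for intervention-versus-control comparisons: the lockdown subgroup in 5.12(b) and the five-phase analysis in 5.16.4, where "The phase participants are categorise in depends on the overlap of their intervention period with pandemic periods of varying restriction". The dose-response sensitivity analysis in 5.16.6 varies only how missing attendance is handled.

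**The concern.** In this model session count is not randomised and there is no control arm, so randomisation gives no protection against calendar time. For part of the retained pandemic cohort the count was limited by lockdown. Some moderate-dose circles were "those that had met 3-4 times face to face and then had little in lockdown". Low counts are therefore more common in one period than in the others.

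Section 5.8 lists "Change of service because of pandemic or relocation" among the intercurrent events, so the SAP recognises that care itself changed. If healthy-baby rates moved in that period for reasons unrelated to sessions, the slope would pick up some of the movement. A fall would look like a benefit of attendance and a rise would look like harm. This is separate from early delivery cutting attendance, because it would arise even if every woman delivered at term.

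Dummy Table 10 will report a coefficient, confidence interval and p-value, which readers may take as support for the intervention's mechanism.

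**Working it through.** The SAP gives no figure for this model, so there is none to reproduce. The phase counts it rests on are consistent.

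**Inputs from the SAP**
- Participants by phase (8.3): 795 + 531 + 176 + 122 = 1624, as stated.
- Intervention women (8.3): 395 as planned; 117 + 154 = 271 high or moderate; 92 low or very low; 63 none. 92 + 63 = 155.
- Post-pandemic target 566 (4.1.2), so about 283 intervention women at 1:1.
- Primary analysis set: 395 + 283 + 271 = 949, of whom 271 (29%) are in the affected phase. With 10% loss (4.1.1), n = 854.
- With the 155 included: 1104 women, of whom 271 + 155 = 426 (39%) are affected.

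**Assumptions, not in the SAP**
- Healthy-baby rate 77% outside the pandemic phase (the 69% plus 8 points of 4.1.1) and 72% within it; no effect of sessions.
- Sessions outside the phase: mean 5.5, SD 2.2. Within it, three cases: mean 3 (SD 1.5), mean 3.6 (SD 2), mean 4 (SD 2.2).

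**Formulas.** Let p = 0.286, p(1−p) = 0.204, d = 0.05, and gap = difference in mean sessions.
- Within-phase variance W = (1−p)·SD₀² + p·SD₁². Between-phase variance B = p(1−p)·gap². Share = B/(W+B).
- The share is the part of the pandemic shift that the slope carries across the gap.
- Outcome variance: mean rate 0.77 − 0.286 × 0.05 = 0.756, so v = 0.756 × 0.244 = 0.185.
- Log odds ratio per session = d·share/(gap·v). Multiply by 8 for 8 versus 0.
- Shift of the test statistic z = d·√(n·p(1−p)·share/v). False-positive rate = Φ(z−1.96) + Φ(−z−1.96).
- Standard-error ratio after adding phase = 1/√(1−share).

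**Mean 3, SD 1.5**
- W = 0.714 × 4.84 + 0.286 × 2.25 = 4.10. B = 0.204 × 6.25 = 1.28. Share = 0.24.
- Log odds ratio = 0.05 × 0.237/(2.5 × 0.185) = 0.0257; × 8 = 0.206; odds ratio 1.23.
- z = 0.75; false positives 11.6%; standard-error ratio 1.145.

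**Mean 4, SD 2.2**
- W = 4.84. B = 0.204 × 2.25 = 0.46. Share = 0.087.
- Odds ratio 1.13; z = 0.45; false positives 7.4%; standard-error ratio 1.05.

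**Simulation.** Rounding sessions and limiting them to 0–8 narrows the spread, so simulated values are slightly higher.

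| Pandemic sessions, 5-point fall | OR, 8 v 0 | False positives |
|---|---|---|
| Mean 3 (SD 1.5) | 1.26–1.27 | 12–14% |
| Mean 3.6 (SD 2) | 1.18 | 9% |
| Mean 4 (SD 2.2) | 1.15 | 7–8% |
| Mean 3, plus the 155 low/no-dose women | – | about 20% |
| Primary set, phase term added | about 1.00 | about 5% |

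In the first case the slope carries about 27% of the shift, and a 5-point rise gives an odds ratio of about 0.78. With no shift the unadjusted slope is unbiased.

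The result depends on the attendance assumption. Binomial attendance (means 3.5–4.5 in high-dose and 1.75–3 in moderate-dose circles; healthy-baby rate 73% outside the phase) gave 1.32–1.36 and 9–19% in the primary set.

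**The case against.** Five points on the other side have weight.

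- **Curtailment was uneven.** Of the 33 circles, 21 (154 women) were moderate dose: 8 met 3–4 times and then had little, 10 met 1–2 times with other components, and 3 never met in person but ran virtual circles. The other 12 (117 of 271 women, 43%) were high dose. All of those met in person, 7 of them four or more times. Section 5.14 does not exclude virtual sessions from the count. A reader might infer that lockdown cut attendance sharply in all 33 circles; Appendix 8.3 does not support that. This stands, and is why milder attendance cases are shown.
- **No outcome shift is shown.** The SAP has no data that healthy-baby rates changed in the pandemic. The rising induction rates listed in 5.8 are not tied to the pandemic there, and induction is not a component of the composite. This stands.
- **Phase adjustment is not a full repair.** Lockdown-forced variation in sessions is not chosen by the woman or caused by early delivery. Conditioning on phase leaves attendance that is self-selected or cut short by preterm birth, which Appendix 8.2 says can cost up to four sessions. In an illustration with no session effect and no pandemic shift, assuming 7% preterm births each losing 2 sessions outside lockdown, the spurious odds ratio for 8 versus 0 rose from 2.0 unadjusted to 2.4 with phase. This stands, and is the reason to report both slopes.
- **A circle random effect,** if fitted, might absorb some of the bias. Section 5.14 specifies none.
- **The analysis is exploratory.** No primary or secondary conclusion rests on it. This limits the importance of the point but does not remove it.

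**Conclusion.** The point holds in a limited form. The model in 5.14 leaves out a variable linked to both session count and calendar period, and no other section supplies it. In the primary analysis set, an assumed 5-point fall with no session effect gives an odds ratio of about 1.15 to 1.27 for 8 versus 0 sessions and 7 to 14% false positives. These figures rest on assumed attendance and an assumed shift; the true size and direction are unknown.

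A reader might infer that the whole pandemic change would be read as a session effect, or that the sign of the slope depends only on the pandemic. Neither follows. Sessions also vary within phase, so only part of a shift passes into the slope (roughly 9 to 27% in the cases above, and up to about 65% under sharper curtailment with the low- and no-dose women included). Nor do the documents show that outcomes worsened. The randomised primary comparison is untouched.

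**What to change.** In 5.14 and its repeats in 5.16.6:

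1. State that the model uses the primary analysis set, so that the 155 low-, very-low- and no-dose intervention women are excluded.
2. Add the phase defined for 5.16.4 as a fixed covariate, as an explicit exception to the covariate rule in 5.5.
3. Report the slope with and without phase in Tables 10 and 15.
4. State beside the result that the within-phase slope still carries bias from self-selection and from early delivery cutting attendance.

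No new data are needed, because phase is already assigned for 5.16.4. The cost is SAP wording, one more row per table, and a slope standard error about 5 to 17% larger in the primary set. The precision lost comes from the between-phase contrast, which is the part open to period confounding.

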5.15 Protocol deviations

Major protocol deviations detailed in the appendix table such as those randomised under the incorrect stratification factor, randomised in error or received the incorrect allocation will be summarised by allocation group. For the purposes of primary analysis, participants will be analysed as they were randomised and the sensitivity of the primary outcome analysis to these assumptions will be explored through sensitivity analyses.

At the time of writing, we are aware of the following protocol deviations:

- Randomisation under incorrect stratification factor
- Incorrect allocation received (controls in intervention)
- Switched circles after first session attended

5.16 Sensitivity analyses

5.16.1 Imputation analyses assessing the uncertainty around the primary outcome analysis estimate

To assess the extent to which study results are affected by missing data, a sensitivity analysis will be performed on imputed data for primary clinical outcome and stratification variables plus baseline characteristics: age, ethnicity, main language and educational level (2). The proportion of missing values for each variable will be assessed using numerical summaries. Univariable associations between missing values of each variable and observed values of other variables will be examined to understand how reliably a missing value might be imputed (3). This will be performed by constructing separate logistic regression models after creating a binary indicator variable for each variable with missing values coded as "1" and non-missing values coded as "0". The most applicable missing data mechanism will be informed by clinical knowledge of independent and dependent variables, reasons for missingness, and relationships between missingness and the observed values of collected variables.

Multivariate Imputation using Chained Equations (MICE) will be used to impute missing data under the expectation that both independent and dependent variables will have missing values and the data will not be monotonic missing (4). MICE replaces missing values with a random sample of plausible, imputed values drawn from their predictive distribution (5). First, an 'imputation' step will be performed, which involves constructing an imputation model that replaces missing data with one set of plausible values. Assuming that missing data are 'Missing At Random', the imputation model will specify a conditional distribution for missing values of each variable given the observed values of other variables. This imputation model will repeatedly replace missing values with a random sample of plausible values, creating a completed dataset with each imputation. The number of imputations (and thus completed datasets generated) will mirror the proportion of participants with at least one

missing value. For example, 25 complete datasets will be generated if 25% of study participants have at least one missing value (6).

A logistic regression model will be used for missing values of binary variables and a multinomial logistic regression model will be selected for missing values of categorical variables with three or more unordered categories. Missing values of categorical variables with three or more ordered categories will be modelled using ordinal logistic regression and a linear regression model will be specified for continuous variables with missing data. Auxiliary variables – that is, variables that are not included in the intended analysis of imputed variables but are the highly correlated with the imputed variables (or its missingness) – will be included in the imputation model (6).

Next, an 'estimation' step will be conducted, whereby specified analyses – as described in sections 5.7 – will be performed separately for each completed dataset that is generated during the imputation step. Finally, a 'pooling' step will be performed, whereby point estimates (e.g., sample means) and measures of precision (e.g., standard deviations) estimated in each dataset will be aggregated using Rubin's Rules to create a final estimate that accounts for between- and within-imputation uncertainty (7).

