4.1 Sample size

4.1.1 Sample size calculation (pre covid)

For the primary outcome ("Healthy baby"), in order to detect a difference in babies born "healthy" of 8% between the control and intervention arm, with 90% power and a 5% significance level, we would require at least 866 women per arm (i.e. 1732 total). This calculation also assumed an outcome proportion of 69% in the control arm, accounts for clustering within the intervention arm with an intra-cluster correlation (ICC) of 0.05 (in the intervention arm), mean group sizes of 8 with cluster size variability assuming Poisson distribution and assumes 10% drop-out in both arms. This sample size provides 84.8% power to detect a difference between arms of 7.3% in our, former primary outcome, spontaneous vaginal birth. Thus, a sample size 1732 is sufficiently powered to detect changes in both the primary outcome and SVD (now a secondary outcome).

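### SAP 5.16.1 does not name allocated arm or circle in the imputation model and imputes the composite whole; run as listed, the missing-data check leans towards no effect

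*SAP*

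**What the plan says.** SAP 5.10 analyses the primary outcome on complete cases, assuming data missing completely at random, and names multiple imputation as the check on that assumption. SAP 5.16.1 describes the check as run on "imputed data for primary clinical outcome and stratification variables plus baseline characteristics: age, ethnicity, main language and educational level".

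On model form, "A logistic regression model will be used for missing values of binary variables"; multinomial, ordinal and linear regressions are given for the other variable types. No multilevel term and no imputation by arm is mentioned. Predictors are described only as other variables, plus unnamed auxiliaries defined as variables lying outside the intended analysis. For the analysis of each completed dataset the section points to SAP 5.7, which is Multiple testing.

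The primary model is in SAP 5.9: an arm effect, a fixed effect for English level, and random intercepts for site and for circle (intervention arm only).

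Under SAP 3.2 the composite is missing when any component is missing, with one exception: when Live baby is recorded as no, the composite is no. Table 11 extends the imputation analysis to spontaneous vaginal delivery.

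**The concern.** An imputation model should contain at least what the analysis model contains. If arm is left out, missing outcomes in both arms are drawn from the same distribution, and each imputed woman contributes no treatment difference. Because allocation is randomised, baseline covariates cannot stand in for it. The imputed estimate would then move towards zero because of the imputation model and not because of the missing data, and a reader comparing the two columns of Table 11 could take the complete-case result to be fragile.

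The second issue is the composite. A baby recorded as preterm, or as admitted to neonatal care, is known not to be healthy. If another component such as the GROW centile is absent, SAP 3.2 still sets the composite to missing, and SAP 5.16.1 then imputes that missing value as a single binary variable. Nothing in the text stops the draw from being healthy.

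**Working it through.** **Inputs.** From SAP 4.1.1: a difference "of 8% between the control and intervention arm, with 90% power and a 5% significance level"; the calculation "assumed an outcome proportion of 69% in the control arm", so 77% with the intervention; ICC 0.05 in the intervention arm; "mean group sizes of 8 with cluster size variability assuming Poisson distribution"; and it "assumes 10% drop-out in both arms". From SAP 5.5: "all p-values will be two-sided". The SAP gives no missing fraction for the primary outcome. The 10% allowance is used as the central value, and 5% and 20% are assumptions.

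**Step 1: reproduce the plan's figure.** With Poisson circle sizes the design effect is 1 + 8 × 0.05 = 1.40. Applied to the intervention arm only, with unpooled variances:

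n = (1.96 + 1.2816)² × (0.69 × 0.31 + 1.40 × 0.77 × 0.23) / 0.08² ≈ 758, and 758 / 0.90 ≈ 843 per arm.

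Pooled variance gives 855. Averaging the design effect over the arms gives 646 × 1.20 / 0.90 ≈ 862. All lie within 3% of the stated 866, so the inputs are read as intended.

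**Step 2: expected effect if arm is omitted.** With 1:1 allocation the pooled rate is 73%. At missing fraction m:

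- intervention: (1 − m) × 77 + m × 73
- control: (1 − m) × 69 + m × 73
- difference: (1 − m) × 8

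| Missing | Intervention % | Control % | Difference (points) | Odds ratio |
|---|---|---|---|---|
| none | 77.0 | 69.0 | 8.0 | 1.50 |
| 5% | 76.8 | 69.2 | 7.6 | 1.47 |
| 10% | 76.6 | 69.4 | 7.2 | 1.44 |
| 20% | 76.2 | 69.8 | 6.4 | 1.39 |

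**Step 3: simulation.** Each scenario used 1,500 trials with 866 controls, 108 circles of Poisson(8) size, and beta-binomial outcomes with ICC 0.05. Outcomes were missing at random by individual or, in the intervention arm, by whole circle. The analysis was a risk difference with cluster-robust variance and Rubin's rules. Ranges cover the two missingness patterns.

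| Missing | Imputation | Mean difference | Rubin SE / empirical SD | Power |
|---|---|---|---|---|
| 5% | arm omitted | 0.076–0.077 | 1.02–1.06 | 0.90–0.92 |
| 10% | arm omitted | 0.072 | 1.09 | 0.87–0.89 |
| 20% | arm omitted | 0.064 | 1.20–1.23 | 0.75–0.79 |
| 5–20% | arm in, circle out | 0.079–0.080 | 0.96–1.02 | 0.88–0.93 |
| 5–20% | arm and circle in | 0.080–0.081 | 0.97–1.04 | 0.86–0.92 |

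Complete-case power was about 0.90 at 10% missing and 0.87–0.88 at 20%. With arm included, leaving out circle made the mean SE about 1% smaller at 5–10% missing (for example 0.0240 against 0.0242) and 2–3% smaller at 20% (0.0252 against 0.0259). Coverage stayed at about 94–95%.

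**Step 4: the composite.** Take a baby recorded as preterm with no GROW centile. Under SAP 3.2 the composite requires every component to be yes, so the true value is no. The same section nevertheless sets it to missing. If the composite is imputed at average plan rates, the baby is drawn as healthy in about 69–77% of imputations, where the correct share is 0%. The SAP does not say how many women this concerns, so the total effect cannot be computed.

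**The case against.** The strongest reply is that the list in SAP 5.16.1 names the variables to be filled in, not the predictors. Allocation is known for every randomised woman and would not appear there. Auxiliaries are defined as variables outside the intended analysis, which makes most sense if the analysis variables, arm included, are already in the model. This reading is fair. A reader might infer that the plan excludes arm; it does not say so. It fails to say that arm is included, and the sentence that should link imputation to analysis points to the wrong section. Even on the generous reading, the prescribed regressions have no circle term.

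A reader might also infer that omitting arm and circle makes the intervals too narrow. The calculation does not support this. Omitting arm makes Rubin's standard error too large (ratio 1.09 at 10% missing), and omitting circle alone shrinks it by only 1–3% with coverage about nominal. Site needs no separate mention, since it is one of the stratification variables already listed.

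The size is also modest. The 10% is a sample-size allowance. SAP 5.4 excludes women who withdraw before delivery from the main analyses, and SAP 5.10 says missing birth data are actively chased. By the plan's own design the standard error is about 8 / 3.24 ≈ 2.5 points, so a 0.8-point shift is about a third of a standard error. This limits the importance of the point but does not remove it.

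On the composite, the unnamed auxiliaries could include the recorded components, which would push such draws towards no. The plan does not state this, and only rebuilding the composite from its components guarantees it.

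**Conclusion.** The point holds as a conditional one. Run as listed, the imputation analysis would be biased towards no effect by about the missing fraction (0.4, 0.8 or 1.6 points of 8 at 5, 10 or 20% missing), with standard errors that are too wide. If arm is in the model, this bias disappears and the missing circle term matters little. Separately, imputing the composite as a whole allows a baby with a recorded failing component to be counted as healthy.

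The figures assume missingness completely at random within arm, no strong covariates, and the SAP's planning rates and ICC. The simulation used a cluster-robust risk difference, not the SAP's mixed logistic model with g-computation. The complete-case primary analysis is untouched; what is at stake is whether the check that SAP 5.10 relies on can be read at face value.

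**What to change.** In SAP 5.16.1:

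- State that imputation is done separately by allocated arm, or that arm is in every imputation model, together with all terms of the analysis model.
- Impute the four components and rebuild the composite in each completed dataset, so that any recorded failing component always gives no.
- As a minor consistency refinement, allow for circle in the intervention arm, for example with a random intercept.
- Point the estimation step to SAP 5.9 in place of 5.7.

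The cost is a few sentences and slightly more complex imputation code. Two-level imputation, if adopted, takes longer to run. No new data are needed and the primary analysis does not change.
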